- Fitting measurements for prism glasses including use of a photograph: After selecting a suitable spectacle frame for the subject a photo will be taken for reference measurements (the photo will only show one eye and the frame around that eye; Figure 3).

[figure not shown]

Figure 3: A reference photo to document the location of the pupil with respect to the frame. The person taking the photo will zoom in as much as possible so that the photo includes only the eye and frame on the side that the prisms will be fitted. If needed, the photo will be cropped to exclude any other facial features. Only the cropped photo will be stored. This photo will be referenced with the subject's study ID code and included with the order for prism glasses sent to Chadwick Optical by study staff at Schepens

- **Eligibility determination**

After Visit 1, study staff at Schepens, supervised by [name] or [name], will review the results of the screening tests and make a decision about eligibility. Eligible participants will then be assigned to sequence AB or BA using minimization by a member of the study team at Schepens and the study site will be informed.

- **Manufacture of prism glasses**

A pair of FPP glasses and a pair of MPP glasses will be manufactured for each eligible participant by Chadwick Optical. Schepens will prepare the order for prism glasses based on the measurements taken at Visit 1 and send the order directly to Chadwick, including the reference photo to document the location of the pupil with respect to the frame. After manufacture, study glasses will be sent by Chadwick Optical to the study site. Study ID codes will be used on all orders for prism glasses (participant names will not be used). We anticipate that it will take about one month for the study glasses to be manufactured and sent to the study sites.

- **Visit 2: Fitting first pair of prism glasses**

- Mobility questionnaire (rate level of difficulty in various situations without prism glasses)
- Fit first pair of glasses
- Photo to document fitting of first pair of prism glasses (includes only the eye and frame on the side the prisms are fitted)
- Training in how to use the first pair of glasses, including a walk through corridors and rooms, accompanied by a member of the research team
- VR walking simulator test (practice without prism glasses)

- **Home use - first pair of prism glasses**

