- Study team members fitting prism glasses, training participants to use prism glasses, and performing data collection will not be masked as it would be impossible to do so. These team members will all be knowledgeable about prism glasses and will easily be able to see whether participants are using the MPP or FPP glasses; the prism glasses have to be worn during data collection for the primary outcome measure. Given that the primary outcome measure is based on objective electronic data (rather than questionnaire data), we believe the risk that data collectors might bias the results is very low. (The primary outcome measure is based on performance in the VR walking simulator pedestrian detection task. Electronic data collected while the participant performs the test will be sent directly to Schepens for processing to derive the primary outcome measure.)

7. Risks and Discomforts

All procedures in this study are minimal risk.

Vision Tests: These are regularly performed for most eye exams.

Prism glasses: There are some risks associated with using the prism glasses, but these are similar to the risks encountered when first wearing bifocal or progressive addition lenses. There may be a period of adjustment to the use of the new prism glasses during which the subject may find mobility more difficult and he/she may experience some discomfort. These risks are minimized by fitting the prism glasses while the subject is seated, taking subjects for a supervised walk so that they can get used to the prism glasses before they take them home, providing take-home instructions on how to use the prism glasses, advising subjects to start by using the glasses in a familiar environment, advising subjects to always carry their regular glasses with them so that they can take the prism glasses off and wear their regular glasses if the prism glasses make them feel uncomfortable in any situation, and advising subjects not to drive or operate heavy machinery when wearing the prism glasses.

VR walking simulator pedestrian detection task: There is a slight risk that some people may experience slight and temporary motion sickness from viewing video backgrounds with simulated motion. There will be programmed breaks in testing sessions, which will help to reduce the risk of motion sickness, and subjects will be able to take a break at any time if they become uncomfortable.

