This definition could include an unanticipated adverse device effect, any serious adverse effect on health or safety or any life-threatening problem or death caused by, or associated with, a device, if that effect, problem, or death was not previously identified in nature, severity, or degree of incidence in the investigational plan or application (including a supplementary plan or application), or any other unanticipated serious problem associated with a device that relates to the rights, safety, or welfare of subjects (21 CFR 812.3(s)).

Reporting Adverse events:

All adverse events whether serious or non-serious, expected or unexpected, will be reported as soon as possible to the PI ([name]) or co-PI ([name]) - by a subject or member of the research team.

They will promptly review documented adverse events to determine 1) if the event should be classified as an adverse event; 2) if there is a reasonable possibility that the adverse event was caused by the study device(s); and 3) if the adverse event meets the criteria for a serious adverse event.

[name] (PI) and [name] (co-PI) will be responsible for determining whether an AE is expected or unexpected. An AE will be considered unexpected if the nature, severity, or frequency of the event is not consistent with the risk information previously described for the study device.

All AEs will have their relationship to the study device assessed. The PI will determine the AE's causality based on the temporal relationship and his/her best judgment. The degree of certainty about causality will be graded using the categories below.

- **Definitely Related** – There is clear evidence to suggest a causal relationship, and other possible contributing factors can be ruled out.
- **Possibly Related** – There is some evidence to suggest a causal relationship. However, other factors may have contributed to the event (e.g., the participant's clinical condition, other concomitant events).
- **Not Related** – There is no reasonable possibility that the study device caused the event, there is no temporal relationship between use of the study device and event onset, or an alternate etiology has been established.

The severity of a non-serious, unexpected adverse event will be graded as follows:

- **Mild adverse event** – Events that do not interfere with the participant's daily activities.

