- **Moderate adverse event** – Events result in a low level of inconvenience or concern with the use of the glasses. Moderate events may cause some interference with regular activities related to mobility.
- **Severe adverse event** – Events interrupt a participant's usual daily activity but not potentially life-threatening or incapacitating. Of note, the term "severe" does not necessarily equate to "serious". (For example: A person suffering a temporarily incapacitating injury such as a sprained ankle due to slipping on snow while wearing the prism glasses, even though the fall was not caused due to wearing the glasses)

Any adverse events that are serious, unexpected and related or possibly related to the study will be reported to the Mass Eye and Ear IRB within 7 calendar days from the time the PI becomes aware of the event. Any unexpected and study-related death will be reported to the Mass Eye and Ear IRB within 24 hours of the PI's knowledge of the event by e-mail or telephone. If there is any doubt as to whether an incident or observation is an AE, the event will be reported to IRB nevertheless based on the schedule described below.

The PI will report events to the IRB based on the following schedule:

- Possibly, Probably, or Definitely Related Expected AE – Report to IRB on annual basis
- Possibly, Probably, or Definitely Related Expected Serious AE – Report to IRB within 7 days
- Possibly, Probably, or Definitely Related Unexpected AE – Report to IRB within 30 days of event
- Possibly, Probably, or Definitely Related Unanticipated Problem – Report to IRB within 7 days of event (24 hours for death or data loss)
- Possibly, Probably, or Definitely Related Unexpected Serious AE – Report to IRB within 7 days of event (24 hours for death)

Unanticipated Problem Reporting

All UAPs involving risks to subjects or others will be reported to the Mass Eye and Ear IRB within 7 calendar days from the time the PI becomes aware of the event. If a UAP or an unexpected Serious AE results in a subject's death or was potentially life-threatening, the PI will notify the Mass Eye and Ear IRB

through e-mail or phone within 24 hours from the time the event is identified. A follow-up report will be submitted if applicable, at a later date when more information is available. For UAPs that result in data loss the PI will notify the Mass Eye and Ear IRB through e-mail or phone within 24 hours from the time the UAP is identified.

Planned safety monitoring

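### Section 10 grades adverse events against the prism glasses but elsewhere refers to the study or its procedures, so simulator-caused events can miss routine IRB reporting

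*Combined protocol and SAP*

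**What the plan says.** Section 10, Reporting Adverse events, sends every AE to the PI or co-PI for a three-step review. The second step asks whether the study device may have caused the event. The section continues: "All AEs will have their relationship to the study device assessed". *Not Related* applies where "There is no reasonable possibility that the study device caused the event", and its last alternative reads "or an alternate etiology has been established". Expectedness has the same reference: an AE is unexpected if its nature, severity or frequency "is not consistent with the risk information previously described for the study device".

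Section 6, Study devices, lists the FPP and MPP glasses and nothing else. The simulator appears later in Section 6 as a data collection method. Section 7 treats it as a separate source of risk, noting that "some people may experience slight and temporary motion sickness from viewing video backgrounds with simulated motion".

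Two other rules in Section 10 use a wider reference. The reporting narrative sets a 7-day limit for AEs that are "serious, unexpected and related or possibly related to the study". The definition of an unanticipated problem judges both relatedness and expectedness against taking part in the research and its procedures.

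The IRB schedule that follows has five lines, four for AEs and one for unanticipated problems. Each begins with a grade of Possibly, Probably or Definitely Related.

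**The concern.** The protocol names a harm that comes from a research-only procedure and then provides a causality scale that asks about something else. Read literally, simulator sickness is not caused by the glasses, and the simulator is itself another established cause, so *Not Related* fits on two counts. The schedule's AE lines then do not apply. The same event can count as related under the unanticipated-problem definition or the narrative, and as unrelated under the scale.

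At stake is whether the IRB's routine reports include harms from the procedure that produces the primary outcome. The simulator is used at three visits, in people aged 7 and over who may need a cane or walker.

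**Working it through.** The plan gives no figure to reproduce. The check traces an event caused by the simulator, and not by the glasses, through the Section 10 rules.

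**References used by each rule**
- Three-step review, causality scale and AE expectedness: the study device.
- Unanticipated problem, relatedness and expectedness: the research and its procedures.
- Narrative rule for serious unexpected AEs and for unexpected deaths: the study.
- Schedule, four AE lines: a related grade, for which the device scale is the only one defined.

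**Trace by type of event**
1. *Non-serious and already described, such as motion sickness.* The grade can be *Not Related*. It is not an unanticipated problem, because the protocol describes it, unless its severity or frequency is unexpected. No schedule line applies, including the annual one.
2. *Non-serious and of a kind not described.* The grade can again be *Not Related*, so the 30-day line does not apply. The event reaches the IRB only if it also suggests greater risk than was previously recognized and so becomes an unanticipated problem.
3. *Serious and unexpected.* Reportable within 7 days under the narrative rule and probably also as an unanticipated problem, although the scale asks only about the device.
4. *Serious but regarded as expected.* The 7-day line needs a related grade, so the event can be missed. This is remote, since Section 7 describes only slight and temporary sickness.
5. *Any event during testing with prisms.* The device may have contributed, so *Possibly Related* is available and the schedule applies.

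**Exposure without prisms.** The planned simulator conditions are Visit 2 practice (1, without prisms), Visit 3 (2, with and without) and Visit 4 (2, with and without): 1 + 2 + 2 = 5. Those without prisms number 1 + 1 + 1 = 3. This counts test conditions for someone who completes all visits. It is not a rate of harm.

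**Expectedness.** Simulator sickness is not device risk information. Read literally, the AE rule makes it unexpected, although Section 7 describes it. If only the causality scale were widened, it would fall under the 30-day line instead of the annual one. Both references therefore need changing.

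**Clause about doubt.** The instruction to report when in doubt concerns whether an occurrence is an AE at all, and it points back to the same schedule. It does not settle relatedness.

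**Category mismatch.** The schedule uses Probably, which the scale lacks. The schedule is an either/or list, so this has no operational effect, but it shows that scale and schedule were not aligned.

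**The case against.** The strongest reply is that the device is not the protocol's only reference and that the important events are covered. This is correct. Unanticipated problems are judged against research procedures and have their own schedule line and reporting section. Unexpected frequency is one of the grounds for calling a problem unexpected. Serious unexpected study-related AEs and unexpected study-related deaths are reportable. A fall at the simulator is not described in Section 7 and could well qualify as an unanticipated problem.

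All AEs go to the PI or co-PI whatever their cause. On-site events are noted on the data sheets and a separate log is kept. Safety issues are reviewed at weekly meetings and by the external safety monitor about twice a year. A reader might infer that simulator harms are lost to oversight or would go unnoticed; these provisions do not support that.

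A reader might also infer that any event in a run without prisms must be graded *Not Related*. That does not follow. At Visit 2 the fitting and training walk are listed before the practice. At Visits 3 and 4 the order is counterbalanced after about four weeks of home use, so a run without prisms may directly follow one with them. *Possibly Related* requires only some evidence and allows for other contributing factors. Nor does the issue reach everyone allocated, since the plan expects 20% to withdraw after allocation.

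The protocol also limits the risk itself: participants may sit, those who stand have a supporting frame, and breaks are programmed and available on request.

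What remains is the gap in cases 1, 2 and 4 of the trace, and the contradiction between references. None of the provisions above removes either.

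**Conclusion.** The point holds as an internal contradiction with a limited practical effect, and it should be corrected. AEs caused by the simulator rather than the glasses can be left out of routine IRB reporting: non-serious described events (annual), non-serious undescribed events that are not unanticipated problems (30 days) and, remotely, serious events regarded as expected (7 days). Serious unexpected study-related AEs, study-related deaths and unanticipated problems still reach the IRB, so this is not a total loss of simulator harms.

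The conclusion assumes that the PI applies the scale as written, and that a related grade in the AE lines of the schedule means a grade on that scale, since no other is defined. The documents give no rate for simulator sickness, so the number of events affected is unknown. The primary outcome, the sample size and the efficacy analysis are not affected.

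**What to change.** Reconcile the rules in Section 10 as follows:
- Record two causality judgements for each AE: relation to the study device, and relation to study procedures, including the VR simulator and the fitting and training walk.
- Apply the IRB schedule if either judgement is at least *Possibly Related*.
- Judge expectedness against all of Section 7, not only the device risks.
- Use one set of causality categories in the scale and the schedule, either defining Probably in the scale or removing it from the schedule.

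The cost is a change of wording in Section 10 and probably one more field on the event form, which is an assumption because the data sheets are attachments not seen here. The downside is that some simulator sickness events will be added to the annual report. No endpoint, sample size or clinical rule changes.
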